10.2 SECONDARY EFFICACY PARAMETERS

The secondary efficacy parameter will be:

- Change from baseline in the 4-week average of daily bowel movement frequency during the treatment period;
- Change from baseline in the 4-week average of daily worst abdominal pain scores during the treatment period;
- Change from baseline in the 4-week average of daily bloating during the treatment period;
- Change from baseline in the 4-week average of number of daily urgent bowel movements during the treatment period;
- The proportion of participants with any fecal incontinence during the treatment period;
- Change from baseline in IBS-QoL total score at the end of the treatment period;
- Change from baseline in serum 7 α C4 levels at the end of the treatment period..

11.0 SAFETY ANALYSES

The safety analysis will be performed using the Safety Population. The safety parameters will include adverse events (AEs), clinical laboratory and vital signs. For each safety parameter of the clinical laboratory and vital sign parameters, the last non-missing safety assessment before the first dose of study treatment will be used as the baseline for all analyses of that safety parameter. Continuous variables will be summarized by number of participants and mean, SD, median, minimum, and maximum values. Categorical variables will be summarized by number and percentage of participants.

11.1 ADVERSE EVENTS

Adverse events will be coded by system organ class and preferred term using the *Medical Dictionary for Regulatory Activities (MedDRA)*, version 20 or newer.

An AE will be considered a treatment-emergent adverse event (TEAE) if it was present after the first dose of study treatment or was present before the date of the first dose of study treatment and increased in severity after the first dose of study treatment. If more than 1 AE was reported before the first dose of study treatment and coded to the same preferred term, the AE with the greatest severity will be used as the benchmark for comparison with the AEs occurring during the study. An AE that occurs after the date of the last protocol-defined study visit (or last contact date if last study visit is missing) will not be counted as a TEAE.

The incidence of participants reporting TEAEs in each participant group will be tabulated by system organ class (SOC) and preferred term; by SOC, preferred term, and severity; and by SOC, preferred term, and relationship to the study drug. If more than 1 event occurs with the same preferred term for the same participant, the participant will be counted only once for that preferred term using the most severe and most related occurrence for the summarizations by severity and by relationship to the study drug.

The distribution of TEAEs by SOC and preferred term, severity, and relationship to study drug will be summarized by participant group.

In addition, the incidence of serious adverse events and events that caused death, if any, will be summarized by participant group, SOC, and preferred term.

A listing of participants who discontinued because of an AE(s) and a listing of participants with serious AEs and participants who died (if any) will be presented.

AEs during the Post-treatment Period will also be included in the listings.

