Before undergoing screening procedures, all potential participants will be informed of their privacy rights and will sign an ICF. Participants will have the opportunity to have any questions answered before signing the ICF. The investigator must address all questions raised by the participant. The investigator will also sign the ICF. After signing the ICF, the participant will undergo the screening assessments and procedures listed in the SoA, including fasting serum 7αC4 testing (if necessary) and clinical laboratory testing (serum chemistry, hematology), to determine eligibility. The inclusion and exclusion criteria requirements will be verified for the participant. Concomitant medication and medical history, including history specifically related to IBS-D, vital signs and weight will be recorded and a physical examination will be performed. Height will be measured only at screening.

A serum pregnancy test will also be performed for all women unless they are surgically sterile or there is a documented history of their postmenopausal status. If the pregnancy test is positive, the participant is not eligible to enter the study.

Eligible participants will be instructed to return to the study site in 1 to 2 weeks for the pretreatment visit.

Pretreatment (Visit 2)

This visit may be combined with the screening visit if results from a fasting serum 7α C4 test or 48-hour fecal BA collection, conducted within 1 calendar year prior to screening, are available at the time of the combined visit or results from fasting serum 7α C4 test are available prior to the start of study treatment. After screening procedures have been performed, eligible participants will enter the pretreatment period. Participants will undergo the pretreatment visit and procedures listed in the SoA. The pretreatment visit will occur approximately 2 to 3 weeks before the first dose of study drug.

The inclusion and exclusion criteria, medical history, concomitant medications, and AEs will be reviewed, vital signs and weight will be measured and recorded. Participants will receive instructions on the use of rescue loperamide.

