9.2.1. Time Period and Frequency for Collecting AE and SAE Information

All AEs/SAEs from the start of treatment until the follow-up visit will be collected at the timepoints specified in the SoA (Section 2), and as observed or reported spontaneously by study participants. Any clinically significant abnormalities persisting at the end of the study will be followed until the AE has resolved.

Medical occurrences that begin before the start of study treatment but after obtaining informed consent will be recorded on the Medical History/Current Medical Conditions section of the eCRF, not the AE section.

All SAEs will be recorded and reported to the sponsor or designee within 24 hours, as indicated in Appendix 4, Section 12.4. The investigator will submit any updated SAE data to the sponsor within 24 hours of it being available.

Investigators are not obligated to actively seek AE or SAE information in former study participants. However, if the investigator learns of any SAE, including a death, at any time after a participant has been discharged from the study, and he/she considers the event to be reasonably related to the study treatment or study participation, the investigator must promptly notify the sponsor.

The method of recording, evaluating, and assessing causality of AEs and SAEs and the procedures for completing and transmitting SAE reports are provided in Appendix 4, Section 12.4.

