- Any abnormal laboratory test results (hematology, clinical chemistry, or urinalysis) or other safety assessments (eg, electrocardiograms [ECGs], radiological scans, vital signs measurements), including those that worsen from baseline, considered clinically significant in the medical and scientific judgment of the investigator (ie, not related to progression of underlying disease)
- Exacerbation of a chronic or intermittent pre-existing condition including either an increase in frequency and/or intensity of the condition
- New condition detected or diagnosed after study treatment administration even though it may have been present before the start of the study
- Signs, symptoms, or the clinical sequelae of a suspected drug-drug interaction
- Signs, symptoms, or the clinical sequelae of a suspected overdose of either study treatment or a concomitant medication. Overdose per se will not be reported as an AE/SAE unless it is an intentional overdose taken with possible suicidal/self-harming intent. Such overdoses should be reported regardless of sequelae.
- Lack of efficacy or failure of expected pharmacological action per se will not be reported as an AE or SAE. Such instances will be captured in the efficacy assessments. However, the signs, symptoms, and/or clinical sequelae resulting from lack of efficacy will be reported as AEs or SAEs if they fulfil the definition of an AE or SAE.

Events NOT Meeting the AE Definition

- Any clinically significant abnormal laboratory findings or other abnormal safety assessments that are associated with the underlying disease, unless judged by the investigator to be more severe than expected for the participant's condition
- The disease/disorder being studied or expected progression, signs, or symptoms (clearly defined) of the disease/disorder being studied, unless more severe than expected for the participant's condition
- Medical or surgical procedure (eg, endoscopy, appendectomy): the condition that leads to the procedure is the AE
- Situations in which an untoward medical occurrence did not occur (social and/or convenience admission to a hospital)
- Anticipated day-to-day fluctuations of pre-existing disease(s) or condition(s) present or detected at the start of the study that do not worsen

Definition of SAE

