16.5 MISSING SEVERITY ASSESSMENT FOR ADVERSE EVENTS

If severity is missing for an AE that started before the date of the first dose of study treatment, an intensity of mild will be assigned. If severity is missing for an AE that started on or after the date of the first dose of study treatment, an intensity of severe will be assigned. The imputed values for severity assessment will be used for the incidence summary; the values will be shown as missing in the data listings.

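### The SAP's TEAE definition has no onset condition, so an unworsened pre-dose event would count as treatment-emergent if it is held in the AE data

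*SAP*

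**What the plan says.** **SAP.** Section 11.1 gives the TEAE rule in two limbs. An AE qualifies "if it was present after the first dose of study treatment or was present before the date of the first dose of study treatment". The second limb carries a condition that the first lacks, namely worsening on treatment: "and increased in severity after the first dose of study treatment". The same paragraph covers several pre-dose AEs coded to one preferred term: "the AE with the greatest severity will be used as the benchmark for comparison with the AEs occurring during the study". It then sets an upper time limit (nothing after the last protocol-defined visit, or the last contact date if that visit is missing), but no lower one. In 16.5 the severity rule splits by onset: "If severity is missing for an AE that started before the date of the first dose of study treatment, an intensity of mild will be" imputed, and severe is imputed for AEs that started on or after that date. In 16.6 missing causality is imputed only for the latter group.

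**Protocol.** Section 9.2.1 states: "All AEs/SAEs from the start of treatment until the follow-up visit will be collected at the timepoints specified in the SoA". It adds: "Medical occurrences that begin before the start of study treatment but after obtaining informed consent will be recorded on the Medical History/Current Medical Conditions" page of the eCRF, and not as AEs. The Visit 2 description in Section 9 says: "The inclusion and exclusion criteria, medical history, concomitant medications, and AEs will be reviewed". Appendix 4 lists among events that are not AEs: "Anticipated day-to-day fluctuations of pre-existing disease(s) or condition(s) present or detected at the start of the study that do not worsen". It does count as AEs the exacerbation of a pre-existing condition and a condition newly detected after dosing, even if it may have existed earlier. Section 10.3.3 leaves the full definition of the safety summaries to the SAP, and the protocol text available gives no TEAE definition of its own.

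**The concern.** A treatment-emergent rule normally separates two groups: events that begin on treatment, and events already there that get worse. SAP 11.1 states the second group properly. The first limb, however, tests presence rather than onset, so it also takes in an event that was there before the first tablet and did not change.

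Safety and tolerability in each cohort are a primary objective, and TEAE incidence by cohort is the main AE output. A misclassified event would be reported as emerging on eluxadoline and would also enter the tables by severity and by relationship. With 12 participants per cohort and no concurrent untreated group, a single participant is visible in every percentage.

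**Working it through.** No figure is stated in the plan on this point, so the check is one of logic, followed by simple arithmetic on the size.

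**1. The rule as written.** Let A = present after the first dose, B = present before the first dose, and C = increased in severity after the first dose. The SAP rule is TEAE = A or (B and C). An event that has increased in severity after the first dose is necessarily present after it, so (B and C) implies A. The rule therefore reduces to TEAE = A. The second limb adds nothing, and the benchmark sentence cannot exclude any AE that is present after dosing.

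**2. Applied to five kinds of event.** The last column replaces A with: not present before the first dose, and started on or after its date.

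| Event | A | B | C | As written | With an onset condition |
|---|---|---|---|---|---|
| Starts after dosing, nothing similar before | yes | no | no | TEAE | TEAE |
| Starts before dosing, worsens after | yes | yes | yes | TEAE | TEAE |
| Starts before dosing, continues unchanged | yes | yes | no | TEAE | not a TEAE |
| Starts and resolves before dosing | no | yes | no | not a TEAE | not a TEAE |
| Resolves before dosing, recurs after at the same or lower severity | yes | no per record, yes per preferred term | no | TEAE | TEAE per record, not a TEAE per preferred term |

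The third row is the error. The fifth shows that an onset condition alone is not enough: its result depends on the unit to which presence before dosing applies. The benchmark sentence works by preferred term, which suggests that unit, but the definition does not say so.

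**3. Whether such records exist.** The two documents do not agree.
- Pointing to none: protocol 9.2.1 collects AEs from the start of treatment and sends occurrences between consent and dosing to Medical History. Appendix 4 keeps unworsened fluctuations of pre-existing conditions out of the AE definition.
- Pointing to some: the SAP 11.1 benchmark and the SAP 16.5 mild imputation are both written for AE records that start before dosing. The Appendix 4 entry on newly detected conditions is a further possible route.
- Neutral: the AE review at Visit 2. It says that AEs are reviewed, not that they are entered on the AE page.

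**4. Size.** Assume that all 12 planned participants in a cohort are dosed, so that the Safety Population denominator is 12. If k of them have an event of the third kind and no other TEAE, any-TEAE incidence in that cohort rises by 100 × k/12 points:
- k = 0: 0 points
- k = 1: 8.3 points
- k = 2: 16.7 points

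The documents give no value for k, and full adherence to protocol 9.2.1 makes it 0.

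**The case against.** The strongest reply is that the protocol already removes the problem. If 9.2.1 is followed, the AE data hold no occurrences that began between consent and dosing, and Appendix 4 excludes unworsened fluctuations of older conditions. A worsening condition would count under either wording. This largely stands: it sets the expected effect at or near zero and is why the point is minor. It does not make the definition right, because the same SAP writes two rules for records that 9.2.1 says should not be there.

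A second reply is that the intended rule is evident. The worsening limb, the benchmark and the split by onset in SAP 16.5 and 16.6 make full sense only if unworsened pre-dose events are excluded, and a careful programmer might code it that way. That also stands as a statement of intent. But the SAP is where the protocol places the definition, and coding the sentence as written gives the other result.

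Third, the missing-date rules for AEs in SAP 16.7 are not shown in the text available, and the table specifications are in a separate document. Either could carry an onset condition. This cannot be excluded, but the defining sentence should be right on its own.

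Finally, the safety analysis is descriptive, with no test or decision rule on TEAEs. True, so a misclassification would distort a reported percentage and not a formal conclusion.

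**Conclusion.** The definition in SAP 11.1 is wrong as written: it lacks an onset condition, and this leaves its own second limb and benchmark without effect. The consequence is conditional. It arises only if pre-dose events are held in the AE data, a matter on which SAP 11.1 and 16.5 differ from protocol 9.2.1. The shift of 8.3 points per participant rests on a denominator of 12 and on that participant having no other TEAE. Severity: minor.

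Three stronger readings are tempting and are not supported:
- A reader might infer that unworsened pre-dose events will in fact be reported as treatment-emergent. Protocol 9.2.1 directs such events away from the AE page, so the number may be zero.
- A reader might take the Visit 2 AE review as proof that pre-dose events are recorded as AEs. It does not say that.
- A reader might assume a prevalence of such events and derive a high chance that at least one of the 24 participants is misclassified. The documents give no prevalence, so any such probability is only the assumption restated, and its range must start at zero.

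The efficacy endpoints and the sample size are not affected.

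**What to change.** In SAP 11.1:
- Reword the first limb so that it covers an AE that *was not present before the first dose of study treatment and started on or after the date of the first dose*.
- Keep the second limb (present before, and increased in severity after).
- State whether presence before dosing is judged per AE record or per preferred term, so that an event which resolves before dosing and recurs afterwards has one defined outcome. The benchmark sentence implies preferred term.

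Across the documents, reconcile SAP 11.1 and 16.5 with protocol 9.2.1 on whether pre-dose events are in the AE data. If they are not, say what the benchmark and the mild imputation are to act on, or remove them. If they are, the protocol's recording rule needs to agree.

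The cost is a few sentences in the SAP and one condition in the AE derivation program, with no new data. The reconciliation may also need a clarification of 9.2.1. The one downside is that TEAE counts may be slightly lower than under the literal rule. Unworsened pre-dose events can stay in the listings, so no information is lost.

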11.2 CLINICAL LABORATORY PARAMETERS

Descriptive statistics for clinical laboratory values (in SI units) at baseline, at end-of-treatment, changes from the baseline to end-of-treatment will be presented by participant group for the following laboratory parameters:

[figure not shown]

Table 11.2–1. Criteria for Potentially Clinically Significant Laboratory Tests

11.3 VITAL SIGNS

Vital signs to be assessed include systolic and diastolic blood pressure (BP), pulse rate, respiration rate and weight.

Descriptive statistics for BP (systolic and diastolic), pulse rate, respiration rate and weight will be presented by participant group and for all participants at baseline, end-of-treatment, and for changes from baseline to end-of-treatment.

Blood pressure and pulse rate values will be regarded as PCS if they meet both the observed value criteria and the change from baseline value criteria. Weight values will be regarded as PCS if they meet either high or low change from baseline value criterion. The number and percentage of participants who have PCS post-baseline vital sign values will be tabulated by participant group. The percentages will be calculated relative to the number of participants who have available baseline values and at least 1 post-baseline assessment. The numerator will be the total number of participants with available non-PCS baseline values and at least 1 PCS postbaseline value.

A supportive listing of participants with PCS end-of-study vital sign values will be provided, including the participant number and baseline and end-of-treatment values, for the Safety Population. In this listing, any participant with PCS value (if any) during the Post-treatment Period will also be included. Criteria for PCS vital sign parameters is provided below in Table 10.3-1.

Table 11.3-1. Criteria for Potentially Clinically Significant Vital Signs

Parameter	Flag	Criteria	
		Observed Value	Change From Baseline
Sitting systolic blood pressure, mm Hg	High	≥ 180	Increase of ≥ 20
	Low	≤ 90	Decrease of ≥ 20
Sitting diastolic blood pressure, mm Hg	High	≥ 105	Increase of ≥ 15
	Low	≤ 50	Decrease of ≥ 15
Sitting pulse rate, bpm	High	≥ 120	Increase of ≥ 15
	Low	≤ 50	Decrease of ≥ 15
Weight, kg	High	—	Increase of $\geq 7\%$
	Low	—	Decrease of $\geq 7\%$

a A postbaseline value is considered potentially clinically significant if it meets both the observed-value and the change-from-baseline criteria.

bpm = beats per minute.

11.4 ELECTROCARDIOGRAM (ECG)

ECG assessment is unavailable in this study.

12.0 HEALTH OUTCOMES ANALYSES

The health outcome data are unavailable in this study.

13.0 **INTERIM ANALYSIS**

No interim analysis will be conducted

14.0 DETERMINATION OF SAMPLE SIZE

The total sample size for this study is 24 participants (12 participants with BAM and 12 participants without BAM). No formal sample size estimation will be calculated because the sample size for this study is not based on statistical consideration.

15.0 STATISTICAL SOFTWARE

Statistical analyses will be performed using version 9.4 (or newer) of SAS on a Linux operating system.

16.0 DATA HANDLING CONVENTIONS

16.1 VISIT TIME WINDOWS

Table 16.1–1 presents the visits assigned for efficacy and safety analyses and the corresponding range of treatment days (window) during which an actual visit may occur.

Table 16.1–1. Visit Time Windows

Derived Visit	Scheduled Visit Day^a	Window
Visit 1 (Screening)		
Visit 2 (Pre-treatment)		
Visit 3 (Baseline)	Day 1	Days \leq 1
Visit 4	Day 15	Days [2, 21]
Visit 5 (End of Treatment ^b)	Day 29	Days \geq 22 and last dose day +1
Visit 6	Day 33	Days \geq last dose day + 2

a Relative to the date of the first dose of treatment period. Day 1 = the date of the first dose of study treatment. There is no Day 0.
b Presented in analysis tables for safety parameters, including but not limited to clinical laboratory values and vital signs.

If the assessment date (if the assessment date is unavailable, use visit date instead) is on or after the date of the first dose of study treatment, the study day is calculated by assessment date – date of the first dose of study treatment + 1. If the assessment date is before the date of the first dose of study treatment, the study day is calculated by assessment date – date of the first dose of study treatment. Therefore, a negative day indicates a day before the start of the study treatment.

If a participant has 2 or more visits within the same window, the last visit with a non-missing value will be used for analysis.

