Participants enrolled in the treatment period will return to the study site for study visits at Week 2, Week 4 (end-of-treatment study visit), and for a post-treatment follow-up study visit at Week 6. Telephone contacts may be made to participants in lieu of an on-site visit at Week 2. A complete schedule of activities (SoA) is provided in Section 2. Participants who discontinue from the study before the Week 4 visit should return to the study site to complete the early termination assessments as soon as possible after stopping the study drug.

During the open-label treatment period, participants will record via the eDiary their daily IBS-D symptoms including stool consistency (BSFS), worst abdominal pain, abdominal bloating, bowel movement frequency, rescue medication usage, number of episodes of urgency in a day, and number of episodes of fecal incontinence, if any.

The actual eDiary data entered by the participants will not be provided to the investigative site staff at any time during the study to prevent any potential bias in subsequent participant entries. However, periodic notifications will be generated to inform the investigator of participants' ongoing compliance with eDiary entries and to alert investigators if participants have experienced episodes of constipation or have required excessive loperamide rescue medication for acute treatment of uncontrolled diarrhea.

The total duration of the study is up to 11 weeks, which includes: screening period (0-2 weeks), pretreatment period (2-3 weeks), 4-week open-label treatment period, and 2-week post-treatment follow-up period. A total of 6 study visits are planned for each participant:

- Screening, Week -3 to -5 (Visit 1) prior to Baseline visit
- Pretreatment, Week -3 to -2 (Visit 2) prior to Baseline visit
- Day 1 (Visit 3; first administration of study drug)
- Week 2 (Visit 4; Week 2 of treatment), may be done by telephone
- Week 4 (Visit 5; end of treatment/early termination)
- Week 6 (Visit 6; post-treatment follow-up)

The study design is presented in [Table 5-1](#).

Table 5-1 Study Design

Period	Screening ^a	Pretreatment ^a	Open-Label Treatment			Post-Treatment
Duration	0-2 weeks	2-3 weeks	4 weeks			2 weeks
Week	Screening	Pretreatment	Baseline	Week 2 ^b	Week 4 (EOT/ET)	Week 6 ^b (Follow-up)
Study Visit	1	2	3	4	5	6
Study Day			1	15 (± 2)	29 (± 2)	Visit 5 + 14 days (± 7)

7 α C4 = 7 α -hydroxy-4-cholesten-3-one; BA = bile acid

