4.0 INTRODUCTION

[figure not shown]
This statistical analysis plan (SAP) provides a more technical and detailed elaboration of the statistical analyses of the efficacy and safety data as outlined and/or specified in the final protocol of Study 3030-401-002 dated 19 Oct 2017 and the most recent amendment dated 17 Apr 2019. Specifications of tables, figures, and data listings are contained in a separate document. The SAP for pharmacokinetic will be prepared separately.

Study 3030-401-002 is a Phase 4, non-randomized, open-label, parallel-group, cohort controlled trial to evaluate the efficacy, safety, tolerability and pharmacokinetics of eluxadoline in participants meeting the Rome IV criteria for IBS-D with and without evidence of BAM. This study will be comprised of a 0 to 2-week screening period, a 2 to 3-week pretreatment period, a 4-week open-label treatment period during which time participants will receive eluxadoline 100 mg BID, and a 2-week post-treatment safety follow-up.

[figure not shown]
There will be 24 participants enrolled in the study, 12 with evidence of BAM and 12 without evidence of BAM. Cohort 1 consists of IBS-D participants with evidence of BAM treated with eluxadoline 100 mg oral tablets BID with food. Cohort 2 consists of IBS-D participants without evidence of BAM treated with eluxadoline 100 mg oral tablets BID with food. The 100 mg BID dose selected for this trial is consistent with US and global labeling for eluxadoline in IBS-D. This non-randomized design is considered most appropriate since the cohort assignment will be based on the determination of BAM status. As far as possible, the 2 cohorts will be matched by age, gender and severity of historic symptoms based on the investigator's discretion.

[figure not shown]
The total duration of the study is up to 11 weeks, which includes: screening period (1-2 weeks), pretreatment period (2-3 weeks), 4-week open-label treatment period, and 2-week post-treatment follow-up period. A total of 6 study visits are planned for each participant: Screening, Week -3 to -4 (Visit 1); Pretreatment, Week -3 to -2 (Visit 2); Day 1 (Visit 3; first administration of study drug); Week 2 (Visit 4; Week 2 of treatment), may be done by telephone; Week 4 (Visit 5; end of treatment/early termination); Week 6 (Visit 6; post-treatment follow-up), may be done by telephone. The end of the study is defined as the date of Visit 6. The schedule of evaluations for Study 3030-401-002 is presented in Table 4-1.

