16.3 REPEATED OR UNSCHEDULED ASSESSMENTS OF SAFETY PARAMETERS

If a participant has repeated assessments before the start of the first treatment, the results from the final non-missing assessment made prior to the start of the study treatment will be used as baseline. If end-of-treatment assessments are repeated or if unscheduled visits occur, the last non-missing postbaseline assessment will be used as the end-of-treatment assessment for generating summary statistics. However, all postbaseline assessments will be used for PCS value determinations, and all assessments will be presented in the data listings.

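### The SAP visit windows do not fit the protocol's Visit 5 (end of treatment/early termination) and Visit 6, so some protocol-compliant Visit 5/ET records are not assigned to End of Treatment

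*SAP*

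**What the plan says.** SAP 16.1 states that Table 16.1-1 "presents the visits assigned for efficacy and safety analyses". It assigns each visit by study day:

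- Visit 4: Days 2 to 21.
- Visit 5 (End of Treatment): Days ≥ "22 and last dose day +1". No operator is printed before the second bound.
- Visit 6: Days ≥ "last dose day + 2", with a scheduled day of 33.

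The table has no row or footnote for early termination. Its only tie rule covers several visits in one window, not one visit that meets two windows.

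SAP 4.0 lists "Week 4 (Visit 5; end of treatment/early termination" as a single visit, as the protocol does. Protocol 5.1 (Table 5-1) puts Visit 5 at Day 29 ± 2 and Visit 6 at "Visit 5 + 14 days" (± 7). Protocol 5.1 and Section 8 ask participants who stop early to complete the EOT/ET assessments. Section 5.1 says as soon as possible after stopping, without a limit in days. For completers, Protocol 9 (Post-treatment, Visit 6) places Visit 6 14 days after the last dose.

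Among the secondary endpoints, SAP 10.2 lists "Change from baseline in IBS-QoL total score at the end of the treatment period" and words 7αC4 the same way. Protocol 9.1.2 collects IBS-QOL at baseline and once more, at Week 4 or ET. SAP 16.3 has a fallback for safety parameters when end-of-treatment assessments are repeated or unscheduled visits occur: "the last non-missing postbaseline assessment will be used as the end-of-treatment assessment for generating summary statistics".

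**The concern.** The protocol defines Visit 5 by what it is (end of treatment or early termination). The SAP table defines it by when it happened. The two agree for a completer seen within a day of the last dose, but not for most early terminators or for some completers seen on schedule.

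A record labelled Visit 5/ET that the table calls Visit 4 or Visit 6 would, on the natural reading, drop out of an endpoint analysed at the end of treatment. For IBS-QOL no other post-baseline value can replace it. The loss could be informative where participants stop for adverse events or lack of efficacy, which are two of the reasons listed in Protocol 8. Early stopping is foreseeable: Protocol 3.3 reports that about half of constipation events occurred in the first 2 weeks, and Protocol 8.1 requires discontinuation for severe constipation. Under Protocol 7.3, participants who discontinue may not be replaced.

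End-of-treatment laboratory and vital-sign changes are exposed where the SAP 16.3 fallback is not triggered. Where it is triggered, it has no upper day limit and could take a follow-up value as End of Treatment.

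**Working it through.** **Inputs.** Let L be the last dose day and d the visit day. From SAP Table 16.1-1: V4 is 2 ≤ d ≤ 21, V5 starts at d = 22, and V6 is d ≥ L + 2. From Protocol Table 5-1: Visit 5 is Day 29 ± 2, that is Days 27 to 31, and Visit 6 is Visit 5 + 14 ± 7. The documents do not fix L for completers, so Days 27 to 30 are assumed.

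**Scheduled days.** Day 15 for Visit 4 and Day 29 for Visit 5 match the protocol. Day 33 for Visit 6 cannot be reproduced:

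- nominal: 29 + 14 = 43
- earliest: 27 + 14 − 7 = 34
- latest: 31 + 14 + 7 = 52
- by the rule of 14 days after last dose, with L = 27 to 29: Days 41 to 43

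Day 33 comes before the earliest permitted day.

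**Reading of the Visit 5 bound.** V6 starts at L + 2, so the likeliest meaning is 22 ≤ d ≤ L + 1. This reading is used below unless stated.

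**Completers: permitted Visit 5 days with d ≥ L + 2**

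| L (assumed) | Days assigned to Visit 6 | Of the 5 permitted days |
|---|---|---|
| 27 | 29, 30, 31 | 3 |
| 28 | 30, 31 | 2 |
| 29 | 31 | 1 |
| 30 | none | 0 |

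**Early terminators.** V5 is empty when L + 1 < 22, that is when L ≤ 20. From L = 21 on, only an ET visit on Day 22 or later and within 1 day of last dose qualifies.

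| L | ET day | Assigned to |
|---|---|---|
| 10 | 11 | Visit 4 |
| 10 | 12 | Visit 4 and Visit 6 |
| 20 | 21 | Visit 4 |
| 20 | 22 | Visit 6 |
| 21 | 22 | Visit 5 |
| 24 | 25 | Visit 5 |
| 24 | 26 | Visit 6 |

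**Other readings of the missing operator.**

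- If V5 means exactly L + 1 (and d ≥ 22), the Visit 6 misassignments above are unchanged.
- If V5 means d ≥ L + 1 (and d ≥ 22), visits on Day 22 or later and two or more days after last dose meet both V5 and V6, so their assignment is undefined.
- Under either of these, a Visit 5 on the last dose day itself, for example Day 29 with L = 29, falls in no window.
- Under all three readings, an ET visit on or before Day 21 is never End of Treatment.

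**Weight of one record.** 1/12 = 8.3% of a cohort.

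**The case against.** The strongest case against has five parts.

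1. **The operator may have been lost in reading the PDF.** Under one reading, late visits fall in two windows rather than being excluded. This stands as a qualification, but neither alternative gives a clean assignment, and the gap up to Day 21 does not depend on the operator.
2. **Exclusion from IBS-QOL is inferred.** SAP 10.2 never says that the derived Visit 5 selects the record, the table's footnote b ties the End of Treatment label to safety tables, and the separate table specifications may hold a rule. This also stands in part. However, the table's opening sentence covers efficacy as well as safety, and the SAP gives no other rule for ET records.
3. **Some of the impact cannot be confirmed.** The timing of 7αC4 is not visible, nor is it clear which tests are done at Visit 6, which may be held by phone. This is correct; the 7αC4 part and the risk of taking follow-up values under SAP 16.3 are conditional.
4. **A limit of last dose + 1 may be a deliberate on-treatment rule.** That is legitimate, but it should then be stated as such. It would not explain why an ET visit one day after a last dose on Day 10 is labelled Visit 4.
5. **The stakes are modest.** This is a 24-participant descriptive pilot, the day counts are not expected losses, and Day 33 assigns nothing because the Visit 6 window is open-ended. All of that is true. It limits the importance of the point but does not remove the inconsistency.

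**Conclusion.** The concern holds. As written, the windows misplace Visit 5/ET records that comply with the protocol. This should be corrected, although it does not threaten the main result.

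- **Certain under any reading:** an ET visit on or before Day 21 is not End of Treatment, and Day 33 contradicts the protocol's Visit 6 timing.
- **Dependent on the likeliest reading of the bound and on an assumed last dose day:** 0 to 3 of the 5 permitted Visit 5 days go to Visit 6 for completers. A Visit 5 on Day 22 or later and no later than last dose + 1 is kept correctly.
- **Exposed:** chiefly IBS-QOL, with less certainty 7αC4, and end-of-treatment laboratory and vital-sign changes where SAP 16.3 is not triggered.
- **Not exposed:** the primary BSFS endpoint and the other eDiary endpoints, which do not use these windows, and potentially clinically significant counts, since "all postbaseline assessments will be used for PCS value determinations".

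The number of participants affected cannot be known from the documents and may be zero. Confidence is medium, because dropping misassigned records is the natural reading rather than a stated rule.

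**What to change.** 1. For IBS-QOL, 7αC4 and the end-of-treatment safety summaries, define End of Treatment as the assessment labelled Visit 5/ET, with priority over the Visit 4 and Visit 6 windows.
2. Define Visit 6 as the labelled follow-up after Visit 5/ET.
3. Add a sentence to SAP 16.3 so that follow-up values do not replace end-of-treatment values.
4. Print the operator for the second Visit 5 bound, and reconcile Day 33 with the protocol.
5. Report days since last dose for each end-of-treatment value, list or flag those beyond last dose + 1 and, if wanted, repeat the summary without them.

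The cost is two or three table rows, a footnote, one sentence in SAP 16.3 and minor reprogramming, with no protocol change. The downside is that the ET visit has no upper time limit, so some end-of-treatment values will be off drug. The flag and the optional repeat summary preserve any on-treatment intent behind the last dose + 1 limit.
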